## Study Summary

Title	Outpatient Foley catheter compared to usual inpatient care for cervical ripening: A non-randomized prospective study
Running Title	Outpatient vs. inpatient cervical ripening
Protocol Number	14-008988
Phase	Pivotal
Methodology	Prospective
Overall Study Duration	24 months
Subject Participation Duration	4-36 hours
Single or Multi-Site	Single site
Objectives	To compare the length of pre-delivery hospitalization in pregnant women undergoing cervical ripening with a Foley catheter in the outpatient setting compared with standard methods administered in the inpatient setting.
Number of Subjects	40 Outpatient Foley Subjects + 160 standard of care subjects Total of 400 women and their babies
Diagnosis and Main Inclusion Criteria	Pregnant women at $\geq$ 37 weeks gestation who are scheduled for induction of labor and who have an unfavorable cervical exam (Bishop score <9 and cervical dilation <3cm)
Study Product, Dose, Route, Regimen	The Foley catheter is a single balloon catheter that is placed transcervically by a provider and inflated with 60cc of normal saline. It mechanically dilates the cervix to 3-4cm over several hours.
Duration of Administration	The device will remain in place until it passes through the cervix, generally when the cervix is dilated to 3-4 cm, which typically occurs 3-12 hours after placement.
Reference therapy	Cervical ripening in the inpatient setting with either a Foley catheter and/or vaginal misoprostol 25 mcg tablets every 4 hours.
Statistical Methodology	The mean time of pre-delivery hospitalization between outpatient Foley catheter and inpatient usual care groups will be compared using a two sample t-test or the nonparametric equivalent Wilcoxon rank sum test. Secondary endpoints will be compared using two sample t-tests or the nonparametric equivalent Wilcoxon rank sum test for continuous endpoints or the chi-Square or Fisher's exact test for categorical endpoints.

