**IV. Protocol for the intervention group (Both Randomized Control Trial and Prospective Study)**

- A. The patient will present to the Family Birth Center at 0730 or 1930.
- B. A nonstress test (NST) will be performed
  - 1. The fetal heart rate (FHR) is observed by external monitoring for at least 20 minutes. The FHR is observed for the presence of accelerations, at least 2 in 40 minutes that peak at least 15 beats per minute above the baseline and last for at least 15 seconds. The absence of at least 2 accelerations in up to 40 minutes is considered nonreactive.
  - 2. A nonreactive NST, the presence of  $\geq 3$  variable decelerations in a 20 minute period, late-appearing decelerations, or any deceleration lasting  $\geq 1$  minute should be considered criteria for exclusion.
- C. An ultrasound will be performed for fetal presentation and amniotic fluid index.
- D. A cervical exam will be performed with calculation of a Bishop score.
- E. The patient will be asked the following standard questions.
  - 1. Are you experiencing any of the following: regular, painful contractions? Decreased fetal movement? Vaginal bleeding? Leakage of fluid from the vagina concerning for rupture of membranes? Fevers or chills?
  - 2. She will be excluded from the trial based on her answers, as described in section 4.2 "Exclusion Criteria."
- F. A Foley catheter will be placed if the following criteria have been met: the nonstress test is reactive, the fetal presentation is cephalic, the amniotic fluid index is 5 centimeters or more, the Bishop score is  $<9$ , the cervical dilation is  $<3$  cm, and she has no other clinical characteristics that exclude her from the trial.
- G. An obstetric provider will place a 16 French Foley catheter through the internal os. The balloon will be inflated with 60cc of normal saline. The distal end of the Foley will be taped to the patient's inner thigh.
- H. The fetal heart rate tracing will be monitored for 1 hour after Foley placement.
- I. The patient will be sent home if the following criteria are met: the fetal heart rate tracing is reactive and category I; there is no evidence of rupture of membranes, spontaneous labor, or vaginal bleeding more than spotting; and maternal vital signs are within normal range.
- J. Pain control options

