  - 1. While the Foley catheter is in place, the patient can use the following non pharmacologic methods to decrease discomfort: warm baths, massage, frequent position changes in a comfortable environment, relaxation techniques, and gentle stretching
  - 2. Pharmacologic methods available to the patient include:
    - (a) Tylenol 1000mg orally q6 hours as needed for pain
    - (b) Morphine 10 mg IM once prior to dismissal
- K. The patient will be instructed to return to the Family Birth Center approximately 12 hours following their Foley bulb placement.
- L. The patient will be given verbal and written instructions as follows:

1. To return immediately to the Family Birth Center if she feels decreased fetal movement, if she is concerned her membranes ruptured, if she has vaginal bleeding more than spotting, if she has regular, painful contractions, if she has severe pain, if she develops a fever of  $\geq 100.4\text{F}$  or  $\geq 38.0\text{ C}$ , or if she develops any symptoms concerning to her.
2. If the Foley catheter is expelled at home, she is to record the time of expulsion. She does not need to return to the Family Birth Center earlier than planned due to expulsion.
3. She will be provided with the 24 hour direct access line for the Family Birth Center to call with any questions or concerns.

M. On arrival to the Family Birth Center at 12 hours later, the induction will be continued.

1. The providing team will decide to proceed with oxytocin and/or artificial rupture of membranes.
2. The oxytocin dose will be increased as determined by the Family Birth Center oxytocin low dose infusion regimen.
3. The patient will have continuous electronic fetal monitoring.
4. The remainder of her care during the first, second, and third stages of labor will be at the discretion of the providing team.
5. If the Foley is still in place when the patient arrives, a provider should gently tug on it. If it does not come out, the providing team may choose to deflate and remove the Foley catheter (and then proceed with artificial rupture of membranes or oxytocin) OR leave the Foley in situ and place vaginal misoprostol.

N. All patients' labor progress will be monitored using a partogram. Cesarean delivery will not be performed for arrest of labor or failed induction unless all criteria have been met as outlined by the Family Birth Center Workgroup protocol made effective 6/2/14.

V. Protocol for the control group (Randomized Control Trial)

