A. If the patient is in the outpatient control group, she will arrive to the Family Birth Center at a standard, predetermined time (typically 0730 or 1930) to undergo induction of labor.

B. Method of cervical ripening

1. The only pharmacologic cervical ripening agent to be used is vaginal misoprostol, 25 mcg every 4 hours with a maximum of six doses.
2. She may or may not have a Foley catheter placed as a method of cervical ripening based upon the providing team's discretion.
3. A Foley catheter will be favored during the cervical ripening phase if there is tachysystole and/or a nonreassuring fetal heart tracing precluding further misoprostol administration, provided the Bishop score is still  $<6$ .

C. After cervical ripening is achieved, oxytocin and/or artificial rupture of membranes will be used at the discretion of the providing team.

D. If oxytocin is used during the labor induction, the dose will be increased as determined by the Family Birth Center Oxytocin low dose infusion regimen.

E. The remainder of her care during the first, second, and third stages of labor will be at the discretion of the providing team.

F. All patients' labor progress will be monitored using a partogram. Cesarean delivery will not be performed for arrest of labor or failed induction unless all criteria have been met as outlined by the Family Birth Center Workgroup protocol made effective 6/2/14.

VI. Protocol for the inpatient usual care group (Prospective Study)

A. All methods of cervical ripening and labor augmentation will be at the discretion of the providing team. Cervical ripening will occur as described above with vaginal misoprostol and a Foley catheter; dinoprostone (vaginal prostaglandin, brand name Cervidil) is infrequently used in the Family Birth Center but would now be an option as well. Oxytocin dosing will be increased by the FBC oxytocin low dose infusion regimen, labor will be monitored using a partogram, and Cesarean delivery will continue to be determined by the criteria as described above.

VII. Follow-up

[figure not shown]
A. Inpatient follow-up

1. We will obtain maternal consent to abstract secondary endpoints as described in section 3.3 from the fetal and maternal electronic medical record.

[figure not shown]
B. Follow-up over 6 weeks

1. Secondary endpoints from section 3.3 will be abstracted from the EMR.  

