    - 3. Cervical dilation at the time of cesarean, if known

4. Stage of labor at the time of cesarean

IV. Maternal outcomes

A. Intrapartum complications

1. Intrapartum fever
2. Chorioamnionitis
3. Suspected or confirmed placental abruption
4. Category II or category III fetal heart tracing requiring in utero resuscitation as documented in the electronic record during the cervical ripening phase only

B. Estimated blood loss at delivery

C. Postpartum hemorrhage: yes/no, if pharmacologic or surgical treatments required

D. Infection (endomyometritis, wound infection, or urinary tract infection within 30 days)

E. Readmission within 6 weeks of delivery and reason

F. Length of inpatient hospital stay (in hours from time of admission to noon on the day of discharge)

V. Fetal outcomes

A. Sex

B. Birth weight (grams)

C. Position at delivery (occiput anterior, occiput posterior, occiput transverse, or unknown)

D. APGAR scores at 1 and 5 minutes

E. Umbilical cord blood gas-pH and base excess

F. Disposition after delivery: level I, II, or III. If II or III, reason for admission.

G. Day of life on which discharge occurred

H. Neonatal death within 30 days and reason

VI. Maternal satisfaction data

A. Average scores for each question on the maternal satisfaction survey (see attached)

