### 3.4 Primary Safety Endpoints

The primary safety outcomes are as follows: heavy vaginal bleeding, severe pain (return to hospital overnight for unrelieved pain), mode of delivery, intrapartum complications (as described above), and fetal outcomes (as described above). These will include overall fetal and maternal survival rates. Based on previous studies, we do not anticipate any difference between safety endpoints in the inpatient vs. outpatient groups.

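### The fetal-tracing safety outcome is counted only during cervical ripening, which outpatient women spend mostly at home without a tracing, so a lower outpatient count would not show safety

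*Combined protocol and SAP*

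**What the plan says.** Section 3.3, item IV.A.4, defines the event as "Category II or category III fetal heart tracing requiring in utero resuscitation as documented in the electronic record during the cervical ripening phase only". Section 3.4 names as primary safety outcomes "intrapartum complications (as described above), and fetal outcomes (as described above"), which brings this item in, and adds that "we do not anticipate any difference between safety endpoints in the inpatient vs. outpatient groups". As a categorical maternal outcome it is compared under section 7.3 by chi-square or Fisher's exact test, with no allowance for time under observation.

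For the outpatient group, section 3.1 IV.H states: "The fetal heart rate tracing will be monitored for 1 hour after Foley placement". A woman who meets the dismissal criteria then goes home, and under IV.K: "The patient will be instructed to return to the Family Birth Center approximately 12 hours following their Foley bulb placement". The Study Summary says of the Foley passing through the cervix: "which typically occurs 3-12 hours after placement". Expulsion at home does not require early return (IV.L.2), and no home fetal monitoring is described. Continuous monitoring is specified once induction resumes after return (IV.M.3).

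The reference therapy in the Study Summary is "Cervical ripening in the inpatient setting with either a Foley catheter and/or vaginal misoprostol 25 mcg tablets every 4 hours". Section 3.1 V.B.3 lets a nonreassuring tracing stop further misoprostol, so some tracing during inpatient ripening is implied. No schedule for it is given.

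No section states when ripening ends. For the randomized control group, V.C says "After cervical ripening is achieved, oxytocin and/or artificial rupture of membranes will be used at the discretion of the providing team", which suggests that it ends at oxytocin or membrane rupture. For an outpatient woman who returns with the Foley in place and is given misoprostol (IV.M.5), the plan does not say whether the added time counts.

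**The concern.** The event can be recorded only while a tracing is running. If the plan is followed exactly, one group is in hospital for the whole counting window and the other is at home for most of it. A shortfall in the outpatient group can then come from missing observation, from a true benefit of the Foley over prostaglandins (section 1.1 gives fewer fetal heart rate changes as a reason for choosing it), or from both. This outcome cannot tell them apart. It could also mask a real excess of events at home.

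This matters because section 1.1 says the study will add safety evidence for moving ripening out of hospital, and a low outpatient count here would be easy to cite for that purpose.

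**Working it through.** **The plan's own figure.** The plan gives no rate, power or sample size for this outcome. Its only power statement for the prospective stage (7.2) concerns the primary endpoint, and it reproduces: 4 / (8 × √(1/40 + 1/160)) = 2.83, and Φ(2.83 − 1.96) = 0.807 (0.804 with the t distribution), against the stated 80%. The present point does not touch it.

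**Observation time, from the documents.** One required traced hour in a typical ripening of 3 to 12 hours is 1/3 to 1/12, or 33% to 8%. The untraced remainder is 3 − 1 = 2 to 12 − 1 = 11 hours.

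**Assumptions.** These are not in the documents:
- the same constant hourly risk L in both groups
- H recorded ripening hours in the comparison group, from 3 to 12
- comparison risk p over those hours of 5%, 10% or 20%
- a share f of outpatient women, 0 or 20%, kept in hospital and recorded like the comparison group; they stay in their assigned group (4.4.2, 7.4), although 4.2 item 6 lists a nonreassuring tracing after placement as an exclusion.

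**Formulas.** L = −ln(1 − p)/H. Outpatient recorded risk = (1 − f)(1 − e^(−L)) + f·p. All 40-versus-160 tables were enumerated exactly, with two-sided Fisher's test at 0.05.

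**Comparison risk held at 10% over H hours.** Expected comparison events are 16 of 160. Equal windows would give 4 of 40.

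| H | f | Expected outpatient events of 40 | Significant in favor of outpatient | Outpatient rate lower |
|---|---|---|---|---|
| 3 | 0 | 1.38 | 16.8% | 94% |
| 6 | 0 | 0.70 | 32.9% | 99% |
| 12 | 0 | 0.35 | 45.9% | 99.8% |
| 3 | 20% | 1.90 | 10.0% | 88% |
| 6 | 20% | 1.36 | 17.2% | 95% |
| 12 | 20% | 1.08 | 22.6% | 97% |
| equal windows | – | 4.00 | 1.2% | 50% |

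At p = 20% the significant share is 28% to 93% (1.6% with equal windows). At p = 5% it is about 1%, but the outpatient rate is lower in 80% to 98% of trials (50% with equal windows).

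**Hourly risk held fixed instead.** The table keeps comparison risk at 10% however few hours are recorded, so a shorter window implies a higher hourly risk. Fixing L = −ln(0.9)/12 = 0.00878 per hour, with f = 0 and 0.35 expected outpatient events of 40:

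| H | Expected comparison events of 160 | Significant in favor of outpatient | Outpatient rate lower |
|---|---|---|---|
| 12 | 16.0 | 45.9% | 99.8% |
| 6 | 8.2 | 1.3% | 95% |
| 3 | 4.2 | 0.0% | 79% |

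**Traced ripening after return.** Suppose 30% of outpatient women return with the Foley in place and receive two misoprostol doses, and this time counts. They then have 1 + 2 × 4 = 9 recorded hours. With p = 10%, outpatient risk = 0.7(1 − e^(−L)) + 0.3(1 − e^(−9L)):
- H = 12: 1.16 of 40 expected, significant in 21%
- H = 6: 2.24 of 40, 7%
- H = 3: 4.22 of 40 (10.5% against 10%), 0.9%; the outpatient rate is lower in only about 45% of trials.

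**How much excess could be masked.** To a linear approximation, outpatient hourly risk must be H / ((1 − f) + f·H) times the comparison risk before expected rates match. That is 3/1.4 = 2.1 (H = 3, f = 20%) to 12/1 = 12 (H = 12, f = 0).

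**Counting from start of ripening to delivery.** Take the hospital hours as monitored time and p = 10% over 16 hours. With 12 outpatient hours (7.2), 3.0 of 40 are expected and 3% of trials are falsely significant. With 16 − 9.6 = 6.4 outpatient hours (the reduction in the first trial described in 1.1), it is 1.7 of 40 and 13%.

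**The case against.** The strongest reply is that the inputs that set the size are absent. Neither the inpatient tracing schedule nor any event rate is in the documents, and with hourly risk fixed and few recorded inpatient hours, false significance almost vanishes. This stands: no single percentage above should be quoted as the plan's error rate.

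A reader might infer that a lower outpatient count follows in every case. The documents do not support that. IV.M.5 allows ripening to continue after return and IV.M.3 provides continuous monitoring then; with 30% of women in that position and only 3 recorded comparison hours, the direction disappears.

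A reader might also infer that harm at home would go unseen. That goes too far. Women are told to return at once for reduced movement, bleeding, severe pain, painful contractions or fever, and have a nonstress test on return (6.3). Early return with its reason, meconium, cesarean indication and urgency, Apgar scores, cord gases, nursery disposition and survival are all recorded without restriction to ripening. None replaces a tracing, but serious compromise has other routes to detection.

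Finally, restricting the count to ripening is a reasonable way to keep later labor events out of a comparison of ripening settings. That justifies keeping the count. It does not make the two windows equally observed.

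**Conclusion.** The point holds as one of unequal ascertainment. A primary safety outcome is counted in a window that is largely unobserved in one group by design, and the planned tests do not correct for it. At equal true risk a lower outpatient count is likely, unless inpatients are traced as little as outpatients or many outpatient women have further traced ripening after return.

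The direction rests on the protocol's schedule plus the inference that inpatients are traced for more than an hour. The size rests on assumptions: at 10% comparison risk, false significance favoring outpatient care runs from about 0% to 46%, depending on recorded comparison hours and on whether cumulative or hourly risk is held fixed.

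The harm is limited to how this one outcome is read. The primary endpoint and its power, mode of delivery, Apgar scores and cord gases are unaffected, and no decision rule rests on this item. It is worth correcting but does not undermine the study.

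**What to change.** 1. In 3.3 IV.A.4, define ripening identically in both groups: from the first agent or Foley placement until first oxytocin, membrane rupture or active labor, with Foley plus misoprostol after return counted as ripening.
2. Add, as a supplementary count, the same event from start of ripening to delivery in both groups.
3. State in 3.4 and 7.3 that hours at home are unobserved and that a lower outpatient ripening-phase count is not evidence of safety.
4. Report monitored hours beside both counts only if the record yields them readily. Abstraction is manual (9.3, Data Management), and summing intermittent tracings for 200 women could be laborious.

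The cost is wording in three sections and one more abstracted count, with no added visits or procedures. Times of Foley, ripening agent, oxytocin, membrane rupture and delivery are already collected (3.3 III.C to F and I).

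The downside is that the start-to-delivery count is diluted by labor events unrelated to the ripening setting and still favors the group with fewer hospital hours (about 3% to 13% false significance at 10% risk). It reduces the bias without removing it, so the statement in step 3 is needed whichever count is reported.

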### 3.4 Primary Safety Endpoints

The primary safety outcomes are as follows: heavy vaginal bleeding, severe pain (return to hospital overnight for unrelieved pain), mode of delivery, intrapartum complications (as described above), and fetal outcomes (as described above). These will include overall fetal and maternal survival rates. Based on previous studies, we do not anticipate any difference between safety endpoints in the inpatient vs. outpatient groups.

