Sciscione et al. performed the first prospective randomized controlled trial comparing the use of a Foley catheter in the inpatient versus outpatient setting [10]. A total of 111 women were enrolled; 61 were randomized to the outpatient setting. All women had a number 16 Foley catheter filled with 30cc of sterile saline placed by sterile speculum exam. The primary outcome was difference in Bishop score from the first cervical exam to the cervical exam the next morning. They found no significant difference in the change in Bishop score, pain scores, or total induction time between the groups. The inpatient admission time was 9.6 hours longer in the inpatient group compared to the outpatient group. Only 8% (n=5) returned overnight for either rupture of membranes or labor.

A similar, more recent trial by Henry et al. compared outpatient Foley catheter placement to inpatient PGE2 vaginal gel in 101 women [11]. The outpatient group spent 11.1 fewer hours in the hospital prior to delivery compared to the inpatient group ( $p < .001$ ). They also felt less pain and got more sleep during cervical ripening. Oxytocin was required for induction more often in the outpatient group. No adverse neonatal or maternal outcomes were associated with outpatient Foley catheter allocation. Only one woman in the outpatient group returned to the hospital earlier than scheduled (for regular, painful contractions).

The trials by Sciscione et al. and Henry et al. have limitations, though. First, neither utilized a standard protocol for labor induction. Second, the inpatient control group was allocated to either Foley usage alone (Sciscione et al.) or prostaglandin PGE2 gel alone (Henry et al.). We believe the most appropriate comparison group is “usual care” wherein women may receive either the Foley catheter or prostaglandins based on patient and provider preference.

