The use of a Foley catheter for cervical ripening in the outpatient setting has the potential for substantial advancement to the induction process for the patient, provider, and healthcare system. The Foley catheter is a safe, inexpensive method of cervical ripening that causes less fetal heart rate effects than other ripening methods [7, 8]. Women may find gratification by being in their home environment during more of their labor course [12]. Providers and healthcare systems may be better able to allocate their resources with decreased length of stay during the early induction phase. A 2013 Cochrane review of outpatient cervical ripening concluded that more studies are required to demonstrate its efficacy and safety in this setting [5]. Our study will provide additional evidence of safety and efficacy to transition cervical ripening to the outpatient setting.

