### 3.3 Secondary Study Endpoints

#### I. Baseline maternal data

##### A. Date of birth

- B. Race and ethnicity
- C. Pre pregnancy body mass index
- D. Gravidity
- E. Parity
- F. Medical comorbidities
- G. Surgical history
- H. Major complications during this pregnancy (i.e. gestational diabetes)
- II. Intervention (outpatient) group data
  - A. Method of Foley catheter insertion: digital or sterile speculum
  - B. Foley catheter expulsion at home: yes/no, time of expulsion
  - C. Return to the Family Birth Center earlier than scheduled and reason (labor, rupture of membranes, decreased fetal movement, vaginal bleeding, pain, fever, or other)
  - D. Bishop score before Foley placement
  - E. Bishop score on the morning of admission for continuation of the labor induction
  - F. First induction method used after admission in the morning
    - a. Oxytocin
    - b. Artificial rupture of membranes
    - c. Oxytocin + artificial rupture of membranes
    - d. If Foley catheter still in place, Foley + oxytocin
- III. Procedural data for both groups
  - A. Gestational age at delivery
  - B. Primary providing team in the Family Birth Center (Obstetrics, Midwifery, or Family Medicine)
  - C. Use of Foley catheter: yes/no, date and time
  - D. Use of pharmacologic cervical ripening: yes/no, date and time, number of doses
  - E. Use of oxytocin: yes/no, date and time, maximum dosage
  - F. Rupture of membranes: spontaneous or artificial, date and time
  - G. Epidural placement: yes/no, date and time
  - H. IV pain medication administration prior to delivery—time, medication, and dose
  - I. Date and time of delivery
  - J. Number who delivered within 12, 24, 36, 48 hours from initiation of cervical ripening
  - K. Number who delivered before midnight of the following day
  - L. Meconium passage prior to delivery: yes/no, thin or thick
  - M. Total number of cervical exams
  - N. Mode of delivery
    - 1. Normal spontaneous vaginal delivery
    - 2. Vacuum assisted vaginal delivery and indication
    - 3. Forceps assisted vaginal delivery and indication
    - 4. Cesarean delivery
  - O. If a cesarean delivery was performed:
    - 1. Indication for cesarean (non-reassuring fetal heart status, umbilical cord prolapse, uterine rupture, placental abruption, failed operative delivery, arrest of dilation, arrest of descent, and other)
    - 2. Type of cesarean—emergent, urgent, or non-urgent (“Alpha,” “Beta,” or “Charlie”)

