### Secondary Hypotheses:

The secondary hypotheses are described below, followed by the statistical tests we plan to utilize.

1. Cesarean delivery rates will not differ between the two groups. This hypothesis will be tested using the Chi-Square or Fisher's exact test. Graphical and statistical methods will be used to show the data descriptively. We will report frequencies and percentages.

2. Maternal outcomes (including but not limited to postpartum hemorrhage, infection, hospital readmission rates, and satisfaction scores) will not differ between the two groups. These hypotheses will be assessed using the Chi-Square or Fisher's exact test for categorical endpoints. For continuous endpoints, a 2-sample t-test or the nonparametric equivalent (Wilcoxon Rank-Sum test) will be used. Graphical and statistical methods will be used to show the data descriptively. For continuous data, we will also report means, medians, standard deviations, and ranges. For categorical data, we will report frequencies and percentages.

3. Fetal outcomes (including but not limited to APGAR scores, umbilical artery pH, and nursery disposition) will not differ between the two groups. These hypotheses will be assessed using the Chi-Square or Fisher's exact test for categorical endpoints. For continuous endpoints, a 2-sample t-test or the nonparametric equivalent (Wilcoxon Rank-Sum test) will be used. Graphical and statistical methods will be used to show the data descriptively. For continuous data, we will also report means, medians, standard deviations, and ranges. For categorical data, we will report frequencies and percentages.

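### Severe pain, a primary safety outcome, is defined as a return to hospital that inpatient controls cannot have; secondarily, ripening-phase tracing events are likely under-counted in outpatients

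*Combined protocol and SAP*

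**What the plan says.** Section 3.4 (Primary Safety Endpoints) names heavy vaginal bleeding and "severe pain (return to hospital overnight for unrelieved pain", followed by "mode of delivery, intrapartum complications (as described above), and fetal outcomes (as described above". No other definition of severe pain is given. The same section adds that "we do not anticipate any difference between safety endpoints in the inpatient vs. outpatient groups".

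The only data field that feeds the pain item is 3.3 II.C, under the heading for intervention-group data: "Return to the Family Birth Center earlier than scheduled and reason (labor, rupture of membranes, decreased fetal movement, vaginal bleeding, pain, fever, or other". Section 3.1 describes controls as ripening in hospital throughout. Outpatients attend at 0730 or 1930 (3.1 IV.A).

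Section 7.3 plans chi-square or Fisher tests for categorical maternal outcomes under the hypothesis "Maternal outcomes (including but not limited to postpartum hemorrhage, infection, hospital readmission rates, and satisfaction scores) will not differ between the two groups". Severe pain is not among the named examples.

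The intrapartum complications in 3.4 are those of 3.3 IV.A. Item 4 there counts Category II or III tracings that needed in utero resuscitation, restricted to the ripening phase and to what the record documents. Outpatients are traced for 1 hour after placement (3.1 IV.H) and are asked to come back about 12 hours after placement (3.1 IV.K). No monitoring at home is described.

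**The concern.** Section 1.1 states the purpose: "Our study will provide additional evidence of safety and efficacy to transition cervical ripening to the outpatient setting". A safety outcome can serve that purpose as a comparison only if both groups can have the event and both are observed for it.

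Severe pain fails the first condition. A control in severe pain is managed on the ward (5.6) and never enters the count, so the item can only count against the outpatient group, whatever the true level of pain in either group. The timing word is a further gap: a woman placed in the morning spends her time at home by day, and it is unclear whether her return for pain qualifies.

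The tracing item strains the second condition, in the other direction. An event that needs a tracing in order to be documented can be missed while no tracing is running, so a lower outpatient count could reflect less observation and not more safety.

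**Working it through.** **The plan's own figure.** The documents give no figure for the safety outcomes. The one related figure is the power in 7.2: 40 and 160 women, SD 8 h, difference 16 − 12 = 4 h, two-sided 0.05.

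- Standard error = 8 × √(1/40 + 1/160) = 1.414 h.
- 4/1.414 − 1.96 = 0.868, so power is 80.7% (80.4% with the noncentral t).
- The stated 80% reproduces, and nothing below changes it.

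**Severe pain as a two-group comparison.** With x returns among 40 outpatients and a structural 0/160, the two-sided Fisher p-value equals C(40,x)/C(200,x), because for these small x no other table is as improbable.

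| Outpatient returns | Calculation | p |
|---|---|---|
| 1/40 | 40/200 | 0.20 |
| 2/40 | 780/19,900 | 0.039 |
| 3/40 | 9,880/1,313,400 | 0.0075 |

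Two returns would be enough for nominal significance if the item were tested.

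**How likely two returns are.** Section 1.1 points to a low rate but gives no rate for pain alone. In one cited trial with 61 outpatients, "Only 8% (n=5) returned overnight for either rupture of membranes or labor". In the other, "Only one woman in the outpatient group returned to the hospital earlier than scheduled (for regular, painful contractions". Taking 1% to 2% as an assumption:

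- P(at least 2 of 40) = 1 − (1−q)^40 − 40q(1−q)^39.
- This is 6.1% at q = 1% and 19.0% at q = 2%.

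**What the item can estimate.** As a one-group proportion it is informative, within wide limits. The exact (Clopper-Pearson) 95% intervals are:

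- 0/40: 0% to 8.8%
- 1/40: 0.06% to 13.2%
- 2/40: 0.6% to 16.9%

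**Tracings.** The Study Summary puts expulsion typically at 3 to 12 h after placement. With 1 h traced and no early return, the traced share of outpatient ripening runs from 1/3 (3 − 1 = 2 h untraced) to 1/12 (12 − 1 = 11 h untraced). Outpatients can still register an event in the traced hour, at an early return, or after the planned return if ripening continues (3.1 IV.M.5 allows for that). Section 6.3 also requires a nonstress test at return. The event rate, the inpatient monitoring time and the end of the ripening phase are not given. Section 3.1 V.B.3 implies that inpatients are under surveillance but does not say how much. The size of the bias therefore cannot be computed.

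**Who stays in the count.** Section 4.4.1 allows a woman to be excluded after placement if the tracing is nonreassuring. Section 4.4.2 keeps women who cross over on meeting exclusion criteria, by intention to treat, and 7.4 keeps all prospective enrollees who do not electively withdraw. Separately, 4.4.1 treats an outpatient who leaves the study plan and chooses an epidural as excluded, and 4.4.2 collects no data from elective withdrawals. The outpatients with the most pain may therefore drop out of the pain data.

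**The case against.** The strongest reply is that no between-group test of severe pain is planned. Section 3.4 voices an expectation and not an analysis, 7.3 does not name the item, and its source field already sits under an intervention-group heading. A return to hospital can only describe women who were sent home. With the low rates in 1.1, a spurious p-value is also not the likely outcome.

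Much of this stands. A reader might infer that the plan commits to an invalid test; it does not, and the p-values above are conditional on someone choosing to run one. What remains is that 3.4 places the item among outcomes spoken of as comparable between groups, neither 3.4 nor 7.3 restricts it to outpatients, and the open-ended list in 7.3 leaves the test available. A low rate makes a misleading p-value rarer but does not make the comparison valid.

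On tracings, the reply is that less monitoring at home is part of the strategy under study, and that no wording can recover events nobody traced. That is fair, and it is why the remedy concerns reporting only. It does not make fewer documented outpatient events evidence of safety.

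It is also tempting to replace the pain item with a comparison of epidural and analgesia use, since both groups have records. That comparison is unequal too: availability differs by setting, and 4.4.1 with 4.4.2 may remove the outpatients in most pain.

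**Conclusion.** The main point holds with high confidence, from the definition alone: the control count for severe pain is 0/160 by construction, so the item carries no information on relative pain. The denominators are the planned prospective numbers. Section 7.4 also analyzes women from the randomized stage and does not say whether the stages are pooled, but a structural zero remains a structural zero in either case.

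The tracing point is secondary and holds with moderate confidence, for direction only. Outpatient events are likely under-ascertained; a reader might infer that they are impossible, or that the bias has a known size, and the documents support neither.

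Two further inferences should be avoided. Large false-positive probabilities for the pain item would need return rates well above 1% to 2%, for which the documents give no basis. Nor can it be assumed that the other primary safety outcomes are free of the problem: fever and suspected abruption are among the intrapartum complications, and at home their detection depends on the woman's own recognition of symptoms (3.1 IV.L.1).

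The primary endpoint and the sample size are not affected.

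**What to change.** **Pain.**

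- In 3.4, restate the item as *unscheduled return for pain before the planned return (outpatient group only)*, which also removes the ambiguity of *overnight*.
- Report n/N with an exact 95% interval from the 3.3 II.C data, and state in 7.3 that it is not tested between groups.
- Count and report outpatients who leave the outpatient plan because of pain, including those who choose an epidural, as far as 4.4.2 allows data collection.
- Show epidural and analgesia use by arm as descriptive context only. Use the 5.6 record of all pain drugs as well as 3.3 III.H, which covers IV drugs only and would miss the IM option in 3.1 IV.J.

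**Tracings.**

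- Report 3.3 IV.A.4 descriptively with monitored hours per arm, and state that fewer outpatient events will not be read as evidence of safety.
- Rest the fetal-safety comparison on outcomes ascertained alike in both arms: Apgar scores, cord gases, nursery level and mode of delivery.
- State that an event in the post-placement hour counts and that the woman stays in the analysis under 4.4.2 and 7.4, and reconcile 4.4.1 with that.

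**Cost.** Wording in 3.4, 3.3 IV.A.4, 7.3 and 4.4.1, a count of pain-related departures from the outpatient plan, and one extra abstracted field (monitored hours during ripening). The price is that neither item yields a between-group p-value.
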